8.3.3.3 Criteria for Termination of the Clinical Trial (Holding Rules)

The trial will be supervised by an independent Data Safety Monitoring Board (DSMB). All final decisions, however, regarding study termination or modification will be decided by the Sponsor and in agreement with the independent DSMB.

The clinical trial will be terminated if

- The DSMB requests termination of the clinical trial based on review of all clinical and laboratory data
- The Sponsor, Regulatory Agency or an EC requests the termination of the clinical trial
- 50% reduction in eGFR is observed. In addition, assessment of this parameter will be performed at the DSMB.

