8.5.2.2.6 Clinical Laboratory Assessments

All laboratory assays will be performed according to the laboratory's normal procedures. Reference ranges will be supplied by the laboratory and used to assess the laboratory data for clinical significance and out-of-range pathological changes. The physician should assess out-of-range laboratory values for clinical significance, indicating if the value(s) is/are not clinically significant (NCS) or clinically significant (CS). Abnormal laboratory values that are unexpected or not explained by the patient's clinical condition may be, at the discretion of the investigator, PI or Sponsor, repeated until confirmed, explained, or resolved as soon as possible.

Details are defined in the Laboratory Manual. The following laboratory assessments will be performed:

Bio-Chemistry

Blood samples for biochemistry will be collected at the time points described in Table 1. The following parameters will be assessed:

Aspartate aminotransferase (AST)	Potassium (K)
Alanine aminotransferase (ALT)	Sodium (Na)
Alkaline phosphatase (AKP)	Albumin (ALB)
Total bilirubin (TBI)	Urea nitrogen (BUN)
Total protein (TP)	Creatinine (Cr)

Uric acid (UA)

eGFR (assessment is calculated according to the formula used in local laboratory)

Hematology / Blood Routine

Blood will be drawn at the time points described in Table 1. The following parameters will be assessed:

Red blood cell (RBC) count

Hemoglobin (Hb)

Hematocrit (HCT) or hematocrit total

Platelet (PLT) count

Classification of white blood cells (WBC)

Inflammatory Indicators

Blood will be drawn at the time points described in Table 1. The following parameters will be assessed:

C- reactive protein (CRP)

ESR

Procalcitonin

Urinalysis

pH (PH)

Urinary Protein (PRO)

Blood (red blood cells (BLD) and white blood cells (LEU))

Glucose (GLU)

Microscopic examination (if blood or protein is abnormal)

Stool routine and occult blood

The following parameters will be analyzed in fresh stool:

Red blood cells (RBC)

Occult blood

White blood cells (LEU)

Myocardial enzymes

The following parameters will be analyzed:

creatinine kinase (CK)

[alpha] - hydroxybutyrate dehydrogenase ([alpha]-HBD)

and isoenzyme (CKMB)

Troponin (cTnI)

lactate dehydrogenase (LDH)

Coagulation function

To assess the coagulation function, the following parameter will be analyzed:

Prothrombin time (PT)

D-dimer

Activated partial thromboplastin time (APTT)

FIB

Assessment of Immune function

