3.4 Assignment of Analysis Sets to Analysis

The FAS serves as the primary efficacy analysis set (as randomized). All efficacy analyses are based on the FAS. The SAF will be used for the evaluation of the safety assessments (as treated) unless stated otherwise. All biomarker analyses are based on SAF (as treated) as well. The PP will only be analyzed for main efficacy outcome measures (as treated).

4 Statistical Evaluation

Continuous variables will be summarized with means, standard deviations, medians, lower and upper quartiles, minimums and maximums. Frequencies and percentages will be used to summarize categorical variables.

The two different treatment groups (groups APN01 and Placebo) will be separately tabulated. Where appropriate total columns will additionally be displayed for the two treatment groups combined.

A detailed description of the planned tables, listings and graphs is given in Appendix A.

Baseline

Baseline is defined as last observation before treatment, i.e. Day 1 value or Screening value if Day 1 value is missing or if Screening and Day 1 is the same day, unless stated otherwise.

Visit terminology

Visit No.	Notation used on the case report form	Notation used for tables, listings and graphs
10	Screening (Day -1)	Screening
150	Unscheduled visit	Screening *
20	Day 1	Day 1
30	Day 2	Day 2
40	Day 3	Day 3
50	Day 4	Day 4
60	Day 5	Day 5
70	Day 6	Day 6
80	Day 7	Day 7
150	Unscheduled visit	Day 8 *
90	FU Day 10	FU Day 10
100	FU Day 14	FU Day 14
110	FU Day 28/EOS	FU Day 28/EOS
130	FU Day 28/EOS Phone Visit	FU Day 28/EOS
170	Russia only: Home Visit FU Day 28/EOS	FU Day 28/EOS
120	Early termination	ET
140	Early termination FU Day 28/EOS	ET
150	Unscheduled visit	Unscheduled visit

ET = Early termination

** IMP administration at Screening and at Day 8 as well as all related assessments (e.g. ECG, Vital signs, etc.) are documented in eCRF as IMP administration or assessment on Unscheduled visit and will be shown in TLGs as IMP administration or assessment on Screening and Day 8 respectively.*

Unscheduled visits will not be included in any tables or graphs, only in listings and will be displayed after all scheduled visits.

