The important risks such as multi-organ failure, hypersensitivity, adverse hemodynamic effects and cardiovascular effects will be documented as AEs and will be listed and tabulated by system organ class and preferred term (MedDRA) for treatment emergent adverse events. The number of events, as well as the number and rate of affected patients will be reported for each treatment group. Pre-treatment emergent adverse events will be listed only.

Vital signs

Vital signs include Systolic blood pressure, Diastolic blood pressure, Heart rate, Body temperature and Respiratory rate.

Basic statistics will be computed for absolute values and the absolute change from baseline.

Vital signs will be tested before and after each dose (within 30 min before/after IMP administration) and only once at the visits without IMP. Baseline is defined as Screening value. Daily mean values of assessments before/after IMP administration will be used for calculation of absolute change from baseline at visits with IMP administration.

Oxygen saturation (part of vital signs, but measured only once per visit)

Oxygen saturation will be presented using basic statistics of absolute values for all visits and change from baseline for all after baseline visits.

Clinical laboratory assessments

All continuous results of laboratory data will be converted to standard unit before any calculation if needed. Conversion of all lab values will be described in a separate document.

Value evaluation (Normal / Abnormal – CS / Abnormal – Not CS) will be summarized for all laboratory parameters using frequency table additionally.

Absolute values as well as absolute change from baseline for the following laboratory data will be analysed by visit using basic statistics:

- Biochemistry: AST (GOT), ALT (GPT), Alkaline Phosphatase (AP), Total bilirubin, Total protein, Uric acid, Potassium, Sodium, Albumin, Urea Nitrogen (BUN), Creatinine, eGFR

(assessment is calculated according to the formula used in local laboratory: CKD-EPI, Cockcroft-Gault or MDRD)

- Inflammatory indicators: C-reactive protein (CRP), ESR, Procalcitonin
- Myocardial enzymes: Creatine kinase (total), CKMB, LDH, [alpha] - hydroxybutyrate dehydrogenase ([alpha] -HBD), Troponin (cTnl), Blood lactic acid
- Hematology: Red blood cells (RBC), Hematocrit, White blood cells (WBC), Hemoglobin, Platelets
- Coagulation: Prothrombin time (PT), Activated partial thromboplastin time (APTT), D-dimer, FIB

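### The SAP pools eGFR from up to three local formulas in one by-visit summary, which adds avoidable noise to the eGFR tables; one central derivation would remove it

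*SAP*

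**What the plan says.** Protocol 8.5.2.2.6 leaves the equation to each site: "eGFR (assessment is calculated according to the formula used in local laboratory". Footnote 7 to Table 1 says the same. SAP 4.5 names the equations that may occur: "assessment is calculated according to the formula used in local laboratory: CKD-EPI, Cockcroft-Gault or MDRD".

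SAP 4.5 sets out the summary as follows: "Absolute values as well as absolute change from baseline for the following laboratory data will be analysed by visit using basic statistics". The biochemistry list beneath it has a single eGFR entry next to the other renal markers: "Urea Nitrogen (BUN), Creatinine, eGFR". The opening of SAP chapter 4 splits tables by arm ("The two different treatment groups (groups APN01 and Placebo) will be separately tabulated") and mentions no split by formula.

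The harmonisation described is for units: "All continuous results of laboratory data will be converted to standard unit before any calculation if needed". Its details are elsewhere: "Conversion of all lab values will be described in a separate document".

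One other place uses eGFR. Protocol 8.3.3.3 includes among the conditions for terminating the trial that a "50% reduction in eGFR is observed", and adds that the DSMB will assess the parameter.

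**The concern.** The three named equations are different functions of creatinine and patient characteristics. Two patients with the same creatinine, age and sex can have different recorded eGFR only because their hospitals use different equations. The size of a change from baseline depends on the equation too. A mean, quartile or mean change pooled over such values has no single scale, and part of its spread reflects the choice of formula, not kidney function.

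This deserves some attention because eGFR is the only laboratory parameter named in the termination criteria, and because Protocol 6.7 reports a fatal acute renal failure in an earlier APN01 study that was judged related to study drug. Readers of the final report are likely to look at the eGFR table. What is at stake is how readable and precise that table is.

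**Working it through.** The plan states no eGFR figure, so there is none to reproduce. The sample size calculation has no bearing on this point. The check compares the planned summary with the data available, then illustrates scale dependence under stated assumptions.

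**Step 1: is a common scale produced anywhere?** SAP 4.5 has one eGFR entry, up to three formulas, tables by arm and visit, and conversion of units. Converting units multiplies a result by a constant that is the same for every patient. It cannot turn one equation's output into another's, because the ratio between two equations can vary with creatinine and patient characteristics. No common derivation, split by formula or sensitivity analysis is stated.

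**Step 2: could a common scale be produced?** Creatinine is in the same biochemistry panel as eGFR (Protocol 8.5.2.2.6; SAP 4.5). Age, sex, ethnicity, height and weight are collected at screening (Protocol Table 1, footnote 1), and SAP 4.2 also tabulates race. The inputs for one central formula are already planned.

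**Step 3: percentage change (assumed exponents).** Write eGFR = c × creatinine^(-b), where c is fixed for a patient and formula. A 50% fall requires (creatinine ratio)^(-b) = 0.5, so the ratio is 2^(1/b).

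| Assumed b | Creatinine rise for a 50% fall, 2^(1/b) | Fall when creatinine doubles, 1 - 2^(-b) |
|---|---|---|
| 1.0 | 2.00-fold | 50% |
| 1.1 | 1.88-fold | 53% |
| 1.2 | 1.78-fold | 56% |

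Even a percentage change measured with one formula throughout depends on which formula it was.

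**Step 4: absolute change (assumed 10% or 20% difference in level).** Take b = 1.0 and a patient at 80 under one formula. A formula reading 10% higher gives 80 × 1.10 = 88, and one reading 20% higher gives 80 × 1.20 = 96. If creatinine doubles, each value halves, so the recorded falls are 40, 44 and 48 for the same event.

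**Step 5: noise in the pooled table (assumed).** Suppose three equally used formulas have scales offset by -D/2, 0 and +D/2, with a within-formula SD of 25. The between-formula variance is (D²/4 + 0 + D²/4)/3 = D²/6.

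| D | D²/6 | Pooled SD, √(625 + D²/6) | Share of variance due to formula |
|---|---|---|---|
| 10 | 16.7 | 25.3 | 2.6% |
| 20 | 66.7 | 26.3 | 9.6% |
| 30 | 150 | 27.8 | 19.4% |

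With a within-formula SD between 20 and 30, the share runs from 1.8% (SD 30, D = 10: 16.7/916.7) to 27.3% (SD 20, D = 30: 150/550). The documents do not say how many sites use each formula, so the trial's own figure cannot be computed.

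**The case against.** The case for leaving the plan alone has several sound parts.

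- **Other renal data.** Creatinine and BUN have their own by-visit summaries. Laboratory evaluations are tabulated as normal or abnormal, abnormal ones are listed, and adverse events are tabulated by system organ class and preferred term. A reader might infer that the whole renal safety assessment mixes scales, but only the eGFR summaries do. This stands.
- **Balance between arms.** Center is a dynamic randomisation factor (Protocol 8.1; SAP chapter 1), so local formulas should be roughly balanced between arms. A reader might infer a biased comparison, and the documents do not support that. This stands.
- **No error rate at stake.** The laboratory summaries are descriptive, and a patient's own series probably uses one formula throughout. This stands, although step 3 shows that the size of the change still depends on the formula.
- **The termination criterion.** A reader might infer that the same kidney injury would meet the 50% criterion at one site and not at another, and that a derivation in the final dataset would cure this. The SAP covers the final analysis only. The criterion operates while the trial runs and is assessed at the DSMB, whose analyses are in a separate plan that is not among the documents. Protocol 8.3.3.3 names no formula and does not say whether one patient or a group is meant. A final-analysis derivation cannot alter how the criterion is applied.
- **Size.** A reader might apply a 20% difference in both directions and conclude that a value of 80 could be recorded as anything from 64 to 96. Those two values differ by 96/64 = 1.5-fold, which exceeds a 10-20% difference between formulas.
- **Unseen documents.** Appendix A and the laboratory conversion document are not available here, so a harmonisation step in one of them cannot be excluded.

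These points limit the reach of the concern. They do not show that pooling unlike equations is preferable when the inputs for a common one are collected.

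**Conclusion.** The point holds for the eGFR summaries in SAP 4.5 and is minor. Values from up to three formulas go into one table of absolute values and absolute changes, and the stated unit conversion does not make them comparable. The consequence is avoidable between-site noise and figures that are hard to interpret, without a clear bias between arms and with no effect on any test.

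The documents give no magnitude. The 2.0-fold versus 1.8-fold contrast assumes exponents between 1.0 and 1.2. The variance shares assume equal use of three formulas, a 10 to 30 unit spread and a within-formula SD of 20 to 30. All are illustrations, not estimates for this trial. The conclusion also assumes that the unseen appendix and conversion document contain no common derivation.

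On Protocol 8.3.3.3 the supportable statement is narrow: it refers to eGFR without saying which one, while two other places allow several.

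**What to change.** In SAP 4.5, state that eGFR will be derived in the analysis dataset for all sites with one prespecified formula from unit-converted creatinine, age and sex. Use that value for the by-visit eGFR summaries and for the shift tables planned in Protocol 8.7.1.2.7. Show the locally reported values in listings only. If Appendix A or the conversion document already provides for this, a cross-reference is enough.

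The cost is one derivation step, with no new data collection. The downside is that derived values will differ slightly from those the sites saw, which a table footnote can explain.

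Separately, reconcile Protocol 8.3.3.3 with Protocol 8.5.2.2.6 and SAP 4.5 as to which eGFR the 50% reduction refers to. No threshold or stopping rule is proposed here.

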⁴ Vital signs include temperature, heart rate, respiration, blood pressure, and oxygen saturation. Vital signs need to be tested before and after each dose (within 30 min before/after IMP administration).

⁵ physical examination could also be documented in the context of the general visit/health status assessment e.g. during a general clinical review

⁶ Pregnancy Test: for FOCP only

⁷ Laboratory tests include the following: in case a local lab cannot perform any of these parameters it should be reported as missing value

- Inflammatory indicators: C- reactive protein (CRP), erythrocyte sedimentation rate (ESR), and procalcitonin.
- Blood routines include: red blood cell (RBC) count, hematocrit (HCT) or hematocrit total, and classification of white blood cells (WBC), hemoglobin (Hb), platelet (PLT) count.
- Urine routine includes: glucose (GLU), pH (PH), urinary protein (PRO), red blood cells (BLD), and white blood cells (LEU).
- Stool routine + occult blood: red blood cells (BLD), white blood cells (LEU), occult blood.
- Blood biochemistry includes: aspartate aminotransferase (AST), alanine aminotransferase (ALT), alkaline phosphatase (AKP), total bilirubin (TBI), total protein (ALB), albumin (ALB), urea nitrogen (BUN), Creatinine (Cr), uric acid (UA), potassium (K), sodium (Na), eGFR (assessment is calculated according to the formula used in local laboratory).
- Myocardial enzymes: creatine kinase (CK) and isoenzyme (CKMB), lactate dehydrogenase (of LDH), [alpha] - hydroxybutyrate dehydrogenase ([alpha] - HBD), troponin (of cTnI).
- Coagulation functions include: prothrombin time (PT), activated partial thromboplastin time (APTT), D- dimer, FIB

⁸ results do not need to be available before randomization, results up to 4 weeks old are acceptable

⁹ 12- lead ECG: within 30 min after IMP administration

¹⁰ Respiration: blood gas analysis (oxygenation index, blood lactic acid) or pulse oximetry.

¹¹ Immune function: immunoglobulin (Ig A, Ig M, Ig G)

¹² Biomarkers comprising (per collection of whole blood 10-12 ml)

1 Li-Heparin blood collection tube (5-6 ml):

1. Plasma equilibrium angiotensin levels: Angiotensin II (Ang II), Angiotensin 1-7 (Ang. 1 -7), Angiotensin 1-5 (Ang 1-5), Angiotensin I (Ang I), Angiotensin 1-9 (Ang 1-9)
2. Aldosterone
3. ACE2 Activity and ACE2 concentration
4. Other exploratory RAAS Biomarkers indicators: specific exploratory indicators will be determined as needed

1 EDTA blood collection tube (5-6 ml):

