6.5 Preclinical Results

In a pharmacology study, GSK2586881 (APN01) (IV at 1 mg/kg) when administered alone or co-administered with angiotensin type 1 receptor blocker losartan (10 mg/kg/d, p.o. via chow) or an ACE inhibitor, captopril (10 mg/kg/d, p.o.), to male spontaneously hypertensive rats (SHR) resulted in a decrease in BP of 7.92 mmHg when compared with rats treated with vehicle alone.

Minimal toxicity has been found in animal studies to date as shown in the Table 5 below.

In the 14-day repeated dose study in cynomolgus monkeys, one female monkey receiving the highest dose, 20.8 mg/kg/day, on Day 12 had 6 Ventricular Premature Complexes (VPCs) including an episode of non-sustained ventricular tachycardia (NSVT) consisting of 3 VPCs (triplet). This finding was considered adverse, and therefore the no observed adverse effect level (NOAEL) for this study was determined to be 8 mg/kg/day.

Table 5: Summarized NOAEL of the toxicology and safety-pharmacology studies

Model	Species	NOAEL (mg/kg/day)
Repeated dose toxicology (2 weeks)	HW rats	20.8 (highest dose tested)
Repeated dose toxicology (4 weeks)	Rhesus monkey	2.5 (highest dose tested)
Repeated dose toxicology (2 weeks)	Cynomolgus monkey	8.0
Cardiovascular & respiratory safety pharmacology	Cynomolgus monkey	8.0
Acute dose toxicology	CD rats	40
CNS interaction study (Irwin test)	CD rats	40

Further information can be found in the investigator's brochure [6].

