8.5.2.2.8 Electrocardiogram

A 12-lead ECG will be performed within 30 min after IMP administration (Table 1). Actual ECG assessment times will be monitored.

At a minimum, the date and time of when the event was performed, the investigator's assessment and the heart rate, RR, PR, QT, and QRS intervals are to be collected. All clinically significant abnormalities will be recorded on the appropriate source documents.

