8.7.1.2.7 Safety Endpoint

The safety evaluations will include analyses of AEs and SAEs, changes in vital signs, clinical laboratory assessments and in ECG parameters. The analysis of safety will be based on the SAF.

AEs

Pre-treatment AEs will be analyzed separately based on all patients included into the trial. AEs will be summarized by system organ class and preferred term according to Medical Dictionary for Regulatory Activities (MedDRA). The number of events, as well as the number and rate of affected subjects will be reported. AEs (system organ class and preferred term) will also be summarized by seriousness, by severity and by relationship to study medication. No statistical testing procedures will be applied to the analysis of AEs.

Individual patient data listings will be provided for all deaths, patients with other SAEs, unexpected adverse drug reactions (as confirmed by the sponsor's drug safety manager), discontinuation of IMP due to AEs, or premature trial termination due to AEs.

Vital signs

For vital signs, body temperature and body weight standard descriptive summary statistics will be calculated at each scheduled time point

Furthermore, standard descriptive summary statistics will be computed for the absolute change from baseline to each scheduled visit up to the last individual time point

Laboratory measurements

Laboratory data will be subjected to both a quantitative analysis (descriptive summary statistics) and qualitative analysis where frequencies of normal, above normal and below normal values will be computed.

The following analyses will be performed:

- Standard descriptive summary statistics will be calculated at each scheduled measuring time point
- Standard descriptive summary statistics will be calculated for the absolute change from baseline to each scheduled visit
- Frequencies of normal, above normal, and below normal values will be computed at each scheduled measuring time point
- Shift tables displaying changes with respect to the normal range between baseline and each scheduled visit will be provided
- A listing of all patients with abnormal (above normal or below normal) values at any time point will be given

Findings from ECG (12-lead)

Frequencies for the respective categories of (ab)normality will be tabulated.

A patient data listing of all clinically significant abnormal ECG values will be provided.

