2.3 Safety Endpoints

- Adverse events (AEs) and serious adverse events (SAEs)
- Vital signs: Systolic blood pressure, Diastolic blood pressure, Heart rate, Body temperature, Respiratory rate
- Oxygen saturation
- Clinical laboratory assessments:
 - Biochemistry
 - Inflammatory indicators
 - Myocardial enzymes
 - Hematology
 - Coagulation
 - Urinalysis
 - Stool routine and occult blood

- ECG parameters: Heart rate [bpm], RR interval [ms], PR interval [ms], QT interval [ms], QRS complex [ms], ECG evaluation
- Detection of viral nucleic acid or viral gene sequencing

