- Urinalysis: pH, Microscopic examination Red blood cells (BLD), Microscopic examination White blood cells (LEU)
- Stool routine and occult blood: Red blood cells (RBC), White blood cells (LEU)

Frequencies will be provided for the following categorical laboratory results by visit:

- Urinalysis: Glucose, Protein, Red blood cells (BLD), White blood cells (LEU)
- Stool routine and occult blood: Red blood cells (RBC), White blood cells (LEU), Occult blood

All abnormal evaluations (CS as well as not CS) for all laboratory assessments collected in eCRF will be listed.

ECG parameters

ECG evaluation (Normal / Abnormal – CS / Abnormal – Not CS) will be summarized using frequency table.

All clinically significant abnormal ECG values inclusive all ECG parameters (Heart rate [bpm], RR interval [ms], PR interval [ms], QT interval [ms], QRS complex [ms]) will be listed as well.

Detection of viral nucleic acid or viral gene sequencing

Detection of viral nucleic acid or viral gene sequencing data will be presented using frequency tables and listing.

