4.9 Miscellaneous

For qualitative variables the frequencies (absolute and relative) are calculated. If no further remark is given in the description of the tables, following format will be used for all tables with qualitative variables (Note: In shift tables the percentages are based on the overall Total and not on the column Totals):

	Y-variable(s) (e.g., treatment group)					
	Category 1		Category 2		Total	
X-variable(s)	N	%	N	%	N	%
Category 1	xx	xx.x	xx	xx.x	xx	xx.x
Category 2	xx	xx.x	xx	xx.x	xx	xx.x
Missing	xx	xx.x	xx	xx.x	xx	xx.x
Total	xx	100.0	xx	100.0	xx	100.0

For this standard format the description of the tables in Appendix A determines only the X- and Y-variables. If another format of table is described in the details to the tables, the real design will be determined by the technical possibilities within SAS and may not look identical to the provided example. However, all information as displayed will be included.

Quantitative parameters will be described by declaring the mean value, standard deviation, minimum, first quartile, median, third quartile, and maximum. In the description of the tables this will be denoted by „basic statistics“. In general, minimum and maximum will be presented to the same level of precision as the raw data; means and medians, standard deviation, and quartiles will be presented to one further decimal place. P-values will be reported to four decimal places (i.e., 0.xxxx).

For frequency tables, all missing values (including user-defined missing values) will be combined in one category “missing” and included in the calculation of percentages. Percentages will be presented to one decimal place.

Tables and graphics will be presented only for scheduled visits.

The listings are always sorted by treatment group, center, and patient. If a different sorting order should be used for some listings this will be remarked separately. The variables for the special listings are explicitly given in the description of listings. All listings will be presented for the safety analysis set, if not stated differently, and indicator variables for further analysis sets, e.g., full analysis set, will be added if needed.

Enrolled but not treated patients (e.g. withdrawal before treatment) will be considered in tables and listings describing disposition of subjects, analysis sets as well as listings of PDs.

The following title will be used for all generated tables, listings, and graphs:

3570: APN01-01-COVID19 – final analysis

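### ECG intervals are named safety endpoints, but the SAP text summarises only a three-level ECG rating, with missing ECGs in the denominator and no rate-corrected QT (minor; cheap to improve)

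*SAP*

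**What the plan says.** **What is collected and named.** Protocol 8.5.2.2.8 requires that the investigator's "assessment and the heart rate, RR, PR, QT, and QRS intervals are to be collected". SAP 2.3 lists among the safety endpoints "ECG parameters: Heart rate [bpm], RR interval [ms], PR interval [ms], QT interval [ms], QRS complex [ms], ECG evaluation". Neither document mentions a rate-corrected QT.

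**What is analysed.** Protocol 8.7.1.2.7 opens with a general sentence: "The safety evaluations will include analyses of AEs and SAEs, changes in vital signs, clinical laboratory assessments and in ECG parameters". Its own ECG paragraph is narrower: it plans frequencies of the normality categories and a listing of clinically significant (CS) abnormal ECGs. SAP 4.5 does the same: "ECG evaluation (Normal / Abnormal – CS / Abnormal – Not CS) will be summarized using frequency table". The listing covers "All clinically significant abnormal ECG values inclusive all ECG parameters". Protocol 8.5.3.2.4 speaks more broadly of listing the 12-lead results by sampling time. In the same SAP section, vital signs (including heart rate) and laboratory values get basic statistics for the value and for change from baseline, and the laboratory listing covers all abnormal results, whether CS or not.

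**Missing data.** SAP 4.9 puts missing values in their own row of every frequency table and has them "included in the calculation of percentages". Footnote 17 of protocol Table 1 waives the Day 28 ECG when that visit is by phone.

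**Timing.** Table 1 marks the Day 1 ECG as pre-dose, and protocol 8.5.2.2 asks for Day -1/1 assessments before dosing. Footnote 9 says "12- lead ECG: within 30 min after IMP administration", and 8.5.2.2.8 agrees with the footnote. SAP section 4 takes the Day 1 value as baseline, falling back on screening.

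**The concern.** Five interval measurements are collected at every scheduled ECG and named as endpoints, but the planned table reduces each ECG to a site judgement with three levels. Interval values are shown only where the site has already called the ECG clinically significant. A modest average change in conduction or repolarisation that leaves most tracings rated normal, or abnormal but not CS, would therefore reach no output planned in the SAP text. Raw QT also depends on heart rate, so even a table of the recorded QT would be hard to read without a correction that RR makes possible.

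The denominator rule is a second, smaller matter. It makes the printed percentage of abnormal ECGs depend on how many ECGs were done, and this can differ between arms.

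Cardiac safety has some standing in this programme. SAP 4.5 counts cardiovascular effects among the important risks, and protocol 6.5 reports ventricular ectopy with a short run of ventricular tachycardia in one monkey at the top dose.

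**Working it through.** The plan states no figure for ECG. Its one computed figure, 93 per group for 50% versus 30% with 80% power, reproduces (93 per arm, power 0.800) and does not bear on this point. The rest is illustration. The 100 per arm is the planned enrolment; abnormal rates, missing shares and interval SDs are assumptions, because the documents give none.

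**1. Which ECG data reach an output in the SAP text**

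| Item | Summary by arm | Individual listing |
|---|---|---|
| Investigator's category | yes | CS abnormal only |
| Heart rate | yes, through vital signs | CS abnormal only |
| PR, QRS, QT, RR | none | CS abnormal only |
| Rate-corrected QT | not derived | none |

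**2. Denominator.** Printed % = true % among assessed × (1 − missing share). This assumes that a patient with no ECG at a visit is counted in the missing row. With true rates of 10% (placebo) and 20% (APN01):

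| Missing, placebo / APN01 | Printed, placebo / APN01 | Difference (points) | Ratio |
|---|---|---|---|
| 0% / 0% | 10% / 20% | 10 | 2.0 |
| 20% / 20% | 8% / 16% | 8 | 2.0 |
| 40% / 40% | 6% / 12% | 6 | 2.0 |
| 20% / 40% | 8% / 12% | 4 | 1.5 |
| 10% / 50% | 9% / 10% | 1 | 1.1 |
| 50% / 10% | 5% / 18% | 13 | 3.6 |

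For example, 0.10 × 0.90 = 9% and 0.20 × 0.50 = 10%. Equal missingness shrinks the difference but keeps the ratio. Unequal missingness can dilute or exaggerate both. Assessed-only denominators give 10% versus 20% in every row.

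**3. What the category loses.** Assume normally distributed intervals, 100 per arm, a 10 ms mean shift, and a cut-off that 10% of controls exceed. Power at two-sided 5% is used only as a measure of information; the SAP plans no ECG test.

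| SD (ms) | 95% CI half-width for mean difference = 1.96 × SD × √(2/100) | Abnormal in shifted arm | Power, mean | Power, category |
|---|---|---|---|---|
| 15 | 4.2 ms | 26.9% | 0.997 | 0.876 |
| 20 | 5.5 ms | 21.7% | 0.942 | 0.623 |
| 30 | 8.3 ms | 17.2% | 0.654 | 0.313 |

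A site's three-level rating is not a fixed cut-off, so the category column is only indicative.

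**4. Why QT needs correction if it is tabulated.** QTcF = QT / RR^(1/3), with RR in seconds. A QT of 380 ms gives 380 / (60/70)^(1/3) = 400 ms at 70 bpm and 380 / (60/100)^(1/3) = 451 ms at 100 bpm.

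**The case against.** The strongest reply is that the SAP does what the protocol's own ECG paragraph asks. A reader who sets the opening sentence of protocol 8.7.1.2.7 against SAP 4.5 might infer that the SAP departs from the protocol. On the summary table the documents do not support that: the same protocol section goes on to plan categories and a CS listing, and the overall evaluation is itself one of the ECG parameters in SAP 2.3. What remains is that protocol 8.5.3.2.4 describes a fuller listing than the SAP provides, and SAP section 5 does not mention the narrowing.

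Other stronger readings also fail.

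- *A serious cardiac signal would go unseen.* Cardiovascular effects are listed and tabulated by system organ class, preferred term and arm, and CS ECGs are listed with all their intervals. Only a sub-threshold shift is lost.
- *The animal finding demands interval means.* It was ectopy, in one animal at 20.8 mg/kg/day, with a stated no-effect level of 8 mg/kg/day against the trial's 0.8 (0.4 twice daily). Mean PR, QRS or QTcF does not measure ectopy. The finding supports attention to cardiac safety in general and no more.
- *The arm with more missing ECGs always looks safer.* The distortion can run either way when missingness is unequal, and the printed missing row lets a reader recover assessed-only percentages. The phone-visit waiver touches Day 28 only; the ECGs on Days 1, 2, 3, 5 and 7 fall outside it.
- *Changing heart rate biases a planned QT table.* No QT table is planned. The correction matters only once intervals are summarised.
- *The Day 1 timing conflict corrupts a planned analysis.* No ECG change from baseline is planned, baseline is defined in principle as the last value before treatment, and a screening ECG exists. The conflict becomes material with the proposed tables.

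Appendix A might also contain an interval table that the text does not mention.

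**Conclusion.** The point holds as a minor, inexpensive improvement. In the SAP text, PR, QRS, QT and RR are endpoints without a summary, and a shift among ECGs rated normal or abnormal-not-CS would not be displayed. Under the assumed SDs of 15 to 30 ms, a tabulated mean difference would be known to within about 4 to 8 ms with 100 per arm, and the category carries clearly less information about a 10 ms shift. The denominator rule can turn a true doubling into a printed ratio anywhere from 1.1 to 3.6 under the assumed missing shares, but this is recoverable from the table. These sizes rest on the assumed rates and SDs, on absent ECGs being counted as missing, and on Appendix A adding no interval table. The documents report no QT, PR or QRS effect of the drug, and nothing here suggests one.

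**What to change.** **SAP 4.5.** Derive QTcF from the recorded QT and RR. Tabulate heart rate, PR, QRS and QTcF by visit and arm, as value and as change from the last ECG before the first dose. Add counts of outlying values against limits that the sponsor fixes before unblinding; neither document currently gives any.

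**SAP 4.9.** For by-visit safety frequency tables, use the patients assessed at that visit as the denominator and print the number missing as a count. State whether a patient with no visit record counts as missing.

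**Day 1 ECG timing.** Reconcile Table 1 and protocol 8.5.2.2 with footnote 9 and 8.5.2.2.8. Footnote 14 allows a first dose on the evening of Day -1, which would make a Day 1 ECG post-dose, so baseline should be chosen by recorded time and not by visit label.

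**SAP section 5.** Record the narrower ECG listing, or restore the listing by sampling time.

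**Cost.** A few descriptive tables and a few SAP sentences, using measurements already collected and no additional ECG. One drawback is that assessed-only percentages describe patients who were alive and available at the visit, so the missing counts must stay beside them.
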